9.2 Secondary Objectives

Cost-effectiveness (CE) analyses will be explored using cost data (i.e., treatment related costs) for 2 fractions of VCB compared to standard of care brachytherapy (3, 4, or 5 fractions). A payer's perspective will be applied for the analysis because the costs relevant to treatments will be considered. Cost for the intervention will be measured for the cost of therapy. If costs related to the intervention occurs in different years, costs will be adjusted to the most recent year US using the medical component of the Consumer Price Index (CPI). If charged amounts relevant to the treatments are available, they will be converted to costs by using cost-to-charge ratios. We will not compare charges or costs between institutions. There will be no publication of financial data from any individual participating site.

The following data will be collected retrospectively at each patient's six month visit:

- Date of First Service
- Total Professional Fees (reported in US dollars)
- Total Technical Fees (reported in US dollars)

*Subgroup analyses using available cost effectiveness data points, beyond those listed above, may be performed for patients treated at the Huntsman Cancer Institute.

Patient reported HRQOL will be utilized for effect (i.e., effectiveness side). The HRQOL measure will be based on the EORTC QLQ-30 Global Health Status and will be used to calculate Quality Adjusted Life Years (QALYs).

An additional secondary analysis is obtained from EN 24 question 48, "Have you felt less feminine due to your disease or treatment." The analysis will compare response between the two arms at the one month time point.

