8 STUDY CALENDAR

Examination	Screening ¹	Brachytherapy	Follow-up ⁶	Follow-up ⁶	Follow-up ⁶	Long term Follow-up ⁶
			1 month +/- 12 weeks	6 months +/- 12 weeks	12 months +/- 12 weeks	24 and 36 months +/- 12 weeks
Informed consent	X					
Medical history	X					
Eligibility criteria	X					
Vital signs	X		X	X	X	
Physical examination	X		X	X	X	
Pelvic exams	X		X	X	X	
WHO/ECOG performance status	X		X	X	X	
QLQ30 Questionnaire²		X	X	X	X	
EN24 Questionnaire²		X	X	X	X	
Collection of Cost Data⁴				X		
Collection of Distance Data⁷					X⁸	
Vaginal Cuff Brachytherapy³		X				
Adverse Event assessments		X	X	X	X	
Chart Review⁵						X
COHORT 2 Only						
COST-FACIT¹⁰			X			
Health Care Expense Survey¹¹		X	X			
NCI Diet History Questionnaire III (DHQ-3)⁹			X			
Physical Activity Questionnaire (ACT24)⁹			X			

1. All Pre-study/Screening procedures should be completed less than or equal to 12 weeks before study treatment.

2. Both the QLQ30 and EN24 questionnaires (appendix E and F) should be administered at baseline (prior to the first brachytherapy fraction) and at the 1 month, 6 month, and 12 month follow-up visits. See section 7.2.1 for guidance on participants experiencing severe emotional distress.
3. Subjects randomized to the control arm will undergo one of the three treatment options described in section 5 over no more than 3 weeks. Subjects randomized to the experimental arm will undergo the treatment described in section 5 over no more than 2 weeks. See Appendix D for treatment planning and dose reporting form.
4. Collection of cost data for analysis is described in section 9.2
5. The PI will continue to review patient medical charts at 24 and 36 months for disease reoccurrence at one of the following locations: vaginal, pelvic, or distant.
6. In person visits are preferred to allow for exams, so almost all visits will be done on site. If a patient is ill or cannot travel, questionnaires and history may be obtained via telemedicine. Missed exams will be considered deviations.
7. Patient's zip code and the location of the treatment facility will be collected and documented by the study staff.
8. If the information is not collected at the 12 month follow up visit, it will be collected at a subsequent time point or from patient's medical record.
9. Completion of the DHQ-3 and ACT24 is strongly encouraged, however, incompleteness will not result in a protocol deviation.

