9 CRITERIA FOR EVALUATION AND ENDPOINT (COHORT 1)

9.1 Primary Objective

Evaluate the non-inferiority of patient HRQOL using the Global Health Status from the QLQ-C30 in the 2 arms one month after treatment.

All patients with a valid baseline and with a follow-up QOL questionnaire at one month post treatment will be included in the analysis. We are accounting for an approximate 5 per cent drop out rate. We anticipate a high compliance rate due to the short follow up interval for the primary endpoint. Patients without valid questionnaires will not be replaced. The baseline questionnaire is considered valid if filled out and dated by the patient before the starting date of trial treatment. Reasons for missing baseline and follow-up questionnaires will be assessed.

For the evaluation of the general quality of life the EORTC (European Organization for Research and Treatment of Cancer) Core questionnaire (QLQ-C30 version 3.0) will be used (Appendix E). The EORTC QLQ-C30 is a multidimensional, cancer-specific quality of life questionnaire developed by the EORTC Study Group on Quality of Life (QOL) for repeated assessments within clinical trials. It is developed in a cross- cultural setting and has been found valid and reliable for quality of life assessments in various cancer populations, irrespective of the specific diagnosis. Optional modules developed for specific diagnostic groups or specific treatment modalities can supplement it. The QLQ-C30 contains five functional scales (physical, cognitive, emotional, social and role functioning), a global health status/quality of life scale, three symptom scales (pain, fatigue and nausea/vomiting), and six single items assessing additional symptoms (dyspnoea, insomnia, loss of appetite, constipation, diarrhoea) and perceived financial impact. For the majority of the QLQ-C30 items a 4-point Likert-type response scale is used. Exceptions are the items for the global quality of life scale (where a 7-point scale is used). All subscale and individual item responses are linearly converted to 0 to 100 scales. A higher score for a functional and global quality of life scales represents a better level of functioning. For the symptom scales and items, a higher score reflects a higher level of symptoms and decreased quality of life.

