10.1.2 Handling of missing items in the Global Health Status

If at least half the items in the Global Health Status are present then the Global Health Raw Score will be calculated as the average of the items that are present. This method is effectively equivalent to replacing missing items by the average of the items that are present, and is a standard method for treating summary scores with missing items. If more than half the items are missing the Global Health Status will be treated as missing. Subjects with missing Global Health Status will be excluded from the primary analysis. This method provides valid estimates provided data is missing at random (MAR). Sensitivity analyses may be performed with multiple imputation used to impute missing data.

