10.1.4 Secondary Endpoints

Vaginal HRQOL evaluation using question 48 of the EORTC EN24: "Have you felt less feminine due to your disease or treatment". This item has a four point scale. Ordinal logistic regression will be used to analyze this question, with one month value as outcome variable, treatment arm as primary predictor, and the baseline value as covariate. A non-inferiority analysis will be performed with margin equal to 6.1 points, which represents approximately $\frac{1}{2}$ standard deviation. Additional exploratory logistic regression analyses will include the values at all time points (baseline, one month, 6 months and 12 months).

Cost effectiveness. Once parameters are computed: 1) mean differences in cost and effect between treatments, 2) variances for differences in costs and effects, and 3) covariance between effectiveness and cost difference, the incremental cost-effectiveness ratio (ICER) or incremental net benefits summarizing the monetary value of the intervention will be calculated.

$$ICER = \frac{Cost_{2\text{ Fractions}} - Cost_{\text{standard care}}}{Effect_{2\text{Fractions}} - Effect_{\text{standard care}}}$$

A CE acceptability curve will be used to quantify and graphically depict uncertainty in the analysis. To consider uncertainty in parameters, probabilistic sensitivity analysis utilizing Monte Carlo simulation (i.e., second-order simulation) will be conducted. To reflect the uncertainties in costs and in effects, a gamma distribution for costs and a normal distribution for effects will be adopted. And univariate analyses will be conducted to consider an uncertainty of one parameter at a time over a range of 95% confidence interval in cost and effectiveness measures.

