APPENDIX E. QUALITY OF LIFE QUESTIONNAIRE (ENGLISH)

EORTC QLQ-C30 (version 3)

We are interested in some things about you and your health. Please answer all of the questions yourself by circling the number that best applies to you. There are no "right" or "wrong" answers. The information that you provide will remain strictly confidential.

Patient Study #: _____

Please fill in your initials: _____

Your birthdate (Day, Month, Year): _____

Today's date (Day, Month, Year): _____

	Not at All	A Little	Quite a Bit	Very Much
1. Do you have any trouble doing strenuous activities, like carrying a heavy shopping bag or a suitcase?	1	2	3	4
2. Do you have any trouble taking a long walk?	1	2	3	4
3. Do you have any trouble taking a short walk outside of the house?	1	2	3	4
4. Do you need to stay in bed or a chair during the day?	1	2	3	4
5. Do you need help with eating, dressing, washing yourself or using the toilet?	1	2	3	4
During the past week:		Not at All	A Little	Quite a Bit
6. Were you limited in doing either your work or other daily activities?	1	2	3	4
7. Were you limited in pursuing your hobbies or other leisure time activities?	1	2	3	4
8. Were you short of breath?	1	2	3	4
9. Have you had pain?	1	2	3	4
10. Did you need to rest?	1	2	3	4
11. Have you had trouble sleeping?	1	2	3	4
12. Have you felt weak?	1	2	3	4
13. Have you lacked appetite?	1	2	3	4
14. Have you felt nauseated?	1	2	3	4
15. Have you vomited?	1	2	3	4
16. Have you been constipated?	1	2	3	4

Please go on to the next page

During the past week:	Not at All	A Little	Quite a Bit	Very Much
17. Have you had diarrhea?	1	2	3	4
18. Were you tired?	1	2	3	4
19. Did pain interfere with your daily activities?	1	2	3	4
20. Have you had difficulty in concentrating on things, like reading a newspaper or watching television?	1	2	3	4
21. Did you feel tense?	1	2	3	4
22. Did you worry?	1	2	3	4
23. Did you feel irritable?	1	2	3	4
24. Did you feel depressed?	1	2	3	4
25. Have you had difficulty remembering things?	1	2	3	4
26. Has your physical condition or medical treatment interfered with your family life?	1	2	3	4
27. Has your physical condition or medical treatment interfered with your social activities?	1	2	3	4
28. Has your physical condition or medical treatment caused you financial difficulties?	1	2	3	4

For the following questions please circle the number between 1 and 7 that best applies to you

29. How would you rate your overall health during the past week?

1 2 3 4 5 6 7

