30. How would you rate your overall quality of life during the past week?

1 2 3 4 5 6 7

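### Section 9.2 calculates QALYs from the QLQ-C30 Global Health Status without a utility conversion or an effect horizon, so a per-QALY result is not defined by the plan

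*Combined protocol and SAP*

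**What the plan says.** Cost-effectiveness is a secondary objective of Cohort 1 (section 1.2.2), where the listed endpoint is procedure cost alone. Section 9.2 adds the effect side: "The HRQOL measure will be based on the EORTC QLQ-30 Global Health Status and will be used to calculate Quality Adjusted Life Years (QALYs". It does not say how the calculation is done.

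The score itself is described elsewhere:

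- Section 9.1: "All subscale and individual item responses are linearly converted to 0 to 100 scales".
- Section 10.1.2, when at least half the items are answered: "the Global Health Raw Score will be calculated as the average of the items that are present".
- Appendix E gives the two items, each answered from 1 to 7: "How would you rate your overall health during the past week" and "How would you rate your overall quality of life during the past week".
- Footnote 2 of the Study Calendar (section 8) says the questionnaires "should be administered at baseline (prior to the first brachytherapy fraction) and at the 1 month, 6 month, and 12 month follow-up visits".

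Section 10.1.4 then feeds the effect into an ICER or incremental net benefit. It plans that "A CE acceptability curve will be used to quantify and graphically depict uncertainty in the analysis" and, for the simulation, that "a gamma distribution for costs and a normal distribution for effects will be adopted". The effect is given no unit and no time period there. The six-month visit named in section 9.2 fixes when cost data are gathered; it is not tied to the effect.

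**The concern.** A QALY is time multiplied by a preference weight on a scale where dead is 0 and full health is 1. The Global Health Status supplies neither factor. It is a self-rating without preference weights, its lowest value is an answer from a living patient, and the plan does not say over which months it is to be accumulated.

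Net benefit and the acceptability curve depend on a price per unit of effect. If the unit is called a QALY but is a rescaled rating, a reader who applies a per-QALY threshold compares unlike quantities. The scale matters most when costs and effects pull in opposite directions, that is, when one arm is cheaper but scores lower, or dearer but scores higher. Two competent analysts following section 9.2 could report quite different ICERs from the same data.

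**Working it through.** **1. The plan's own figure on this scale.** The documents state no utility, QALY or ICER value, so there is none to reproduce. The one design figure on the Global Health Status scale is the evaluable sample size of 96 (section 10.1.6: SD 22.2, margin 15, true difference 0, one-sided alpha 0.025, 90% power). The normal approximation gives 2 × (1.960 + 1.282)² × 22.2² / 15² ≈ 46.0, rounded up to 47 per arm, or 94 in total. With 48 per arm, the noncentral t gives power 0.906. The figure reproduces and does not depend on the QALY.

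**2. What the score is.** Two items from 1 to 7 are averaged and converted linearly: score = 100 × (average − 1)/6. With both items answered, one step on one item is 100/12 = 8.3 points. With only one answered, which section 10.1.2 allows, a step is 100/6 = 16.7 points. Score 0 means the lowest rating. No preference weights enter at any stage.

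**3. Effect of the horizon.** The documents do not state score/100; it is used here only as an illustration. For a constant difference of 5 points (assumed):

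| Horizon | Calculation | Result |
|---|---|---|
| 1 month | 0.05 × 1/12 | 0.004 |
| 6 months | 0.05 × 6/12 | 0.025 |
| 12 months | 0.05 × 12/12 | 0.05 |

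The spread is 12-fold.

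**4. Effect of the horizon on the sign.** Assume arm differences of 0 at baseline, −5 at month 1, and +5 at months 6 and 12. At one month the effect is −5 points. The trapezoid area to 12 months is:

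- months 0-1: (0 − 5)/2 × 1 = −2.5
- months 1-6: (−5 + 5)/2 × 5 = 0
- months 6-12: (5 + 5)/2 × 6 = 30

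The total is +27.5 point-months, or 27.5/(100 × 12) ≈ +0.023 as score/100. The same data are unfavourable at one month and favourable over twelve.

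**5. Effect of the missing anchor.** Assume utility = a + (1 − a) × score/100, where a is the utility of the worst rating (not given in the documents). Relative to score/100, a QALY difference is multiplied by (1 − a) and an ICER by 1/(1 − a):

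- a = −0.2: 1/1.2 = 0.83
- a = 0.2: 1/0.8 = 1.25
- a = 0.4: 1/0.6 = 1.67

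**6. Both together.** Take an assumed cost difference of 1,000 dollars and a constant 5 points:

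- 12 months, a = 0: 1,000/0.05 = 20,000 dollars per QALY.
- 1 month, a = 0.4: 1,000/(0.05 × 0.6/12) = 400,000 dollars per QALY.

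That is a 20-fold range, and the documents do not choose within it. These values show that the quantity is undetermined; they do not predict the trial's result.

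**The case against.** The best defence has four parts. Section 9.2 describes the cost-effectiveness work as something to be explored. The endpoint listed in 1.2.2 is cost only. The wording of the QALY sentence leaves room for a mapping to utility. Section 4.2 reports that the Cohort 1 analysis is finished, and the documents do not show whether a cost-per-QALY figure was ever produced.

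All of this stands, and it limits the weight of the point. It does not remove it. A mapping that is permitted but not named leaves the effect undefined, and the missing conversion and horizon are not explained by redaction.

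A reader might infer more: that the plan divides the score by 100 and so overstates QALY differences by a known factor. The documents do not support this. No section says score/100 will be used, and both the size and the direction of any mis-scaling rest on an assumed anchor (step 5).

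A reader might also infer the opposite reassurance, that only the size of the effect is open and its sign is secure. That would follow for a constant difference under a positive linear conversion. With the horizon open and differences free to change over time it does not follow, as step 4 shows.

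**Conclusion.** The point holds in a limited form. The plan names QALYs as the effect measure, but the score it uses has no preference weights and no anchor at death, and neither a conversion nor an effect horizon is given. A figure labelled per QALY on that basis would not be a QALY result and could not be set against a per-QALY threshold. The illustrated size is 12-fold across the three horizons, and 20-fold when an assumed anchor of 0 to 0.4 is added. The 5 points, the 1,000 dollars, the linear utility and score/100 are assumptions.

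The consequence is confined to the ICER, net benefit and acceptability curve. The primary non-inferiority test, the sample size and the plain comparison of procedure costs do not use the QALY. Nor do the documents show that any reported cost-effectiveness conclusion is wrong.

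**What to change.** Replace the QALY sentence in section 9.2 in one of two ways.

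- **Default.** Drop the term QALY. Report the cost difference with its confidence interval beside the one-month Global Health Status difference with its confidence interval, one month being the primary time point. Give the 6- and 12-month differences as supportive. Label any ratio, net benefit or acceptability curve as per Global Health Status point at the time point used. This needs nothing from outside the documents, and section 10.1.4 already plans the cost and effect differences and their variances. The price is that per-QALY comparison with other treatments is given up.
- **Alternative**, only if a validated preference-based scoring or mapping from the collected QLQ-C30 items is available. Name it, and take the area under the curve over a stated horizon, for example baseline to 12 months. State how deaths and missing questionnaires enter, and add one sensitivity analysis on the mapping. The price is that the result depends on the mapping chosen.

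Neither route needs new data. Because the Cohort 1 analysis is complete, mark the change as post hoc and relabel any cost-per-QALY figure that already exists.

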9.3 Exploratory objectives

Evaluate CTCAE v5.0 toxicities

Routine safety and tolerability will be evaluated from the results of reported signs and symptoms, scheduled physical examinations, vital sign measurements, and clinical laboratory test results.

Evaluate and compare doses to organs at risk

Doses to organs at risk including bladder, rectum, sigmoid colon, and urethra, and target in the two trial arms will be evaluated from CT data sets without contours that will be sent to HCI in an anonymized fashion and compared to each other. Artificial intelligence approaches to aid in contouring will be considered. Additionally, the dose to prescribed target in each group will be calculated.

Compare total distance traveled to the cancer center for study related visits.

Total distance traveled, calculated by multiplying number of study visits by twice the distance to the cancer center. The distance to the cancer center will be calculated as the distance from the patient's zip code and the cancer center zip code.

Physical Examination

Complete and symptom-directed physical examinations will be performed by a licensed physician (or physician's assistant or nurse practitioner).

Vital Signs

Vital signs (blood pressure, respiratory rate, pulse rate and temperature) will be obtained.

Compare local recurrence and document patterns of recurrence

Local recurrence will be assessed by pelvic exam. Time points for evaluation include screening, one, six, and twelve months via study visits, and via chart review at twenty-four, and thirty-six months post treatment. Imaging may be used at the physician's discretion depending on the subject's symptoms. Recurrences in the 2 arms will be assessed according to site: vaginal, pelvic, or distant.

Report vaginal, bowel, and bladder symptoms on HRQOL using the EORTC EN24 the two treatment arms.

In addition to the QLQ C-30 core questionnaire, the EORTC module for endometrial cancer EN24 will be used to descriptively report values for the following symptom scores; "Sexual/vaginal problems," "Gastrointestinal symptoms," and "Urological symptoms." Additional questions regarding sexual symptoms and distress will also be reported.

9.4 Stopping Rules

If four discrete subjects present with grade 3 vaginal, rectal, or bladder toxicities considered related to brachytherapy in the experimental arm, it will result in trial closure.

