14.3 Data and Safety Monitoring Plan

A Data and Safety Monitoring Committee (DSMC) is established at Huntsman Cancer Institute (HCI) and approved by the NCI to assure the well-being of patients enrolled on Investigator Initiated Trials that do not have an outside monitoring review. Roles and responsibilities of the DSMC are set forth in the NCI approved plan. The activities of this committee include a quarterly review of adverse events including SAEs, important medical events, significant revisions or amendments to the protocol, and approval of cohort/dose escalations. If the DSMC and/or the PI have concerns about unexpected safety issues, the study will be stopped and will not be resumed until the issues are resolved. The DSMC also reviews and approves audit reports generated by the Research Compliance Office.

This is a multicenter, phase III study classified as high risk per the NCI-approved DSM plan. Each high-risk study will be assigned a physician member of the DSMC as medical monitor, or in rare cases, an external medical monitor. The medical monitor will be notified of all serious adverse events (SAEs). Specific notifications will also be issued when a dose-limiting toxicity is encountered and when the MTD dose is defined. Approval of the medical monitor is required for all dose escalations. All serious adverse events (SAEs) occurring in patients treated at HCI or its affiliates will also be reviewed by the full DSMC monthly. The full committee will also review all toxicities for patients on treatment and less than or equal to 30 days of their last treatment on a quarterly basis.

Each high-risk study will also be assigned a dedicated research compliance officer who will monitor the trial. High-risk studies will be monitored by RCO personnel after the first patient is enrolled and every three months thereafter during active enrollment. The RCO monitor will review the study status and summarize enrollment, toxicities, SAEs, dose escalation, statistical endpoints (e.g., stopping rules), deviations, etc. for the full DSMC membership at the regularly scheduled meetings. Amendments that increase risk, change dosing, or impact study objectives will be reviewed by the DSMC and approved by the PRMC and IRB. High-risk trials will be formally reviewed by the DSMC after the first patient is enrolled and then quarterly thereafter.

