14.4.1 Adverse Events (AE)

An adverse event is the appearance or worsening of any undesirable sign, symptom, or medical condition occurring after starting the study drug even if the event is not considered to be related to study drug. For the purposes of this study, the terms toxicity and adverse event are used interchangeably. Medical conditions/diseases present before starting study drug are only considered adverse events if they worsen after starting study drug. Abnormal laboratory values or test results constitute adverse events only if they induce clinical signs or symptoms, are considered clinically significant, or require therapy.

Collection of adverse events will begin at start of brachytherapy and continue for 12 months after the start of brachytherapy.

Information about all adverse events, whether volunteered by the subject, discovered by investigator questioning, or detected through physical examination, laboratory test or other means, will be collected and recorded and followed as appropriate.

Adverse events should be evaluated to determine:

1. The severity grade based on CTCAE v.5.0 (grade 1-5).
2. Its relationship to the study treatment(s) (definite, probable, possible, unlikely, not related).
3. Its duration (start and end dates or if continuing at final exam).
4. Action taken (no action taken; study treatment temporarily interrupted; study treatment permanently discontinued due to this adverse event; concomitant medication taken; non-drug therapy given; hospitalization/prolonged hospitalization).
5. Whether it constitutes an SAE.

All adverse events will be treated appropriately. Such treatment may include changes in study drug treatment as listed in the dose modification section of this protocol (see section 6.1 for guidance). Once an adverse event is detected, it should be followed until its resolution, and assessment should be made at each visit (or more frequently, if necessary) of any changes in severity, the suspected relationship to the study drug, the interventions required to treat it, and the outcome.

All adverse events will be immediately recorded in the patient research chart.

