14.4.2 Serious Adverse Event (SAE)

Information about all serious adverse events will be collected and recorded.

A serious adverse event is an undesirable sign, symptom or medical condition which:

- Is fatal or life-threatening
- Results in persistent or significant disability/incapacity
- Is medically significant, i.e., defined as an event that jeopardizes the patient or may require medical or surgical intervention to prevent one of the outcomes listed above
- Causes congenital anomaly or birth defect
- Requires inpatient hospitalization or prolongation of existing hospitalization, unless hospitalization is for:
 - Routine treatment or monitoring of the studied indication, not associated with any deterioration in condition (procedures such as central line placements, paracentesis, pain control).
 - Elective or pre-planned treatment for a pre-existing condition that is unrelated to the indication under study and has not worsened since the start of study drug.

- Treatment on an emergency outpatient basis for an event not fulfilling any of the definitions of a SAE given above and not resulting in hospital admission.
- Social reasons and respite care in the absence of any deterioration in the patient's general condition.

SAE evaluation will begin after the first treatment and will continue until the first follow up visit, 28 days (+/- 14) after the completion of study treatment. If the patient is unable to attend the first follow up visit, the SAE reporting period will be extended to 56 days after the completion of study treatment.

Any death from any cause while a patient is receiving treatment on this protocol or up to 30 days after the last dose of protocol treatment, or any death which occurs more than 30 days after protocol treatment has ended but which is felt to be treatment related, must be reported.

Toxicities which fall within the definitions listed above must be reported as an SAE regardless if they are felt to be treatment related or not. Toxicities unrelated to treatment that do NOT fall within the definitions above, must simply be documented as AEs in the patient research chart.

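### The trial-closure rule in section 9.4 counts only grade 3 toxicities, so read literally a subject whose only related event is grade 4 or 5 does not count; it should say grade 3 or higher

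*Combined protocol and SAP*

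**What the plan says.** Section 9.4 gives one rule: "If four discrete subjects present with grade 3 vaginal, rectal, or bladder toxicities considered related to brachytherapy in the experimental arm", the trial is closed. Closure is mandatory once the count is reached. The rule names a single grade, with no *or higher*, no inequality sign and no range.

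Section 14.4.1 requires every adverse event to be graded on CTCAE v5.0 from 1 to 5 and assessed for its relationship to study treatment. It treats toxicity and adverse event as the same thing. It also sets the collection period: "Collection of adverse events will begin at start of brachytherapy and continue for 12 months after the start of brachytherapy".

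Section 14.3 adds a general safeguard. If the Data and Safety Monitoring Committee (DSMC) or the principal investigator "have concerns about unexpected safety issues, the study will be stopped and will not be resumed until the issues are resolved". The same section has the medical monitor notified of every SAE, the full DSMC reviewing SAEs monthly, and a compliance monitor summarising toxicities and the status of stopping rules for the committee. Section 14.5 requires SAE reports within one business day.

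Section 9.4 belongs to section 9, whose heading is limited to Cohort 1. Section 4.2 says that Cohort 1 enrollment and data analysis are complete and that Cohort 2 follows the same design with added outcome measures.

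**The concern.** CTCAE grades 4 and 5 are separate categories from grade 3. A rule that counts subjects with grade 3 events does not, on its wording, count a subject whose only related vaginal, rectal or bladder event was grade 4 or 5. The rule is therefore less sensitive to the worse outcome.

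The protocol writes direction into its other thresholds: a QLQ-C30 score at or below 71 in section 7.2.1, a FACIT-Cost score below 14 in section 7.2.2, and a life expectancy above 2 years in section 5.1.5. Section 9.4 lacks this, and no other section supplies it.

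What is at stake is patient protection in the experimental arm, not the primary comparison. The rule is applied at up to six centres and summarised for the DSMC by a compliance monitor, who has only the written text to check against. It should not depend on each reader supplying the missing words.

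**Working it through.** The documents state no operating characteristics for the rule, so there is no figure to reproduce. The check is to apply the wording as it stands.

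**Inputs.** Threshold of 4 subjects, grade 3, related, experimental arm (section 9.4). Grades 1 to 5 (section 14.4.1). Experimental-arm sizes of 54 in Cohort 1 and 40 in Cohort 2 (Study Summary).

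**Step 1: apply the rule to cases.** All events are related vaginal, rectal or bladder toxicities in the experimental arm.

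| Subjects | Count as written | Closes? | Count with grade 3 or higher | Closes? |
|---|---|---|---|---|
| 4 with grade 3 | 4 | yes | 4 | yes |
| 3 with grade 3, 1 with grade 4 only | 3 | no | 4 | yes |
| 4 with grade 4 or 5 only | 0 | no | 4 | yes |
| 4 with grade 3, one of whom later worsens to grade 4 | 4 | yes | 4 | yes |

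**Step 2: where the two versions differ.** Let X be the number of subjects with at least one related grade 3 event, and Y the number whose only related events are grade 4 or 5. As written, the trial closes if X ≥ 4. Corrected, it closes if X + Y ≥ 4. Because Y ≥ 0, the corrected rule closes whenever the written one does. They differ only when X ≤ 3 and X + Y ≥ 4.

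**Step 3: can the difference be sized?** Not from the documents. They give no combined rate for the three sites, no grade 4-5 rate and no Cohort 1 event count. The nearest figure is the 1.9% grade 3 vaginal toxicity rate in section 3.1. It covers one site only and comes from the brachytherapy arm of an earlier randomised trial, whose regimen section 3.1 describes as a higher biologic dose.

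For illustration only, assume independent subjects, use 1.9% for X, and add an assumed 0.5%, 1% or 2% for Y. With p the probability that a subject counts,

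P(at least 4) = 1 − Σ(k = 0 to 3) C(n,k) p^k (1 − p)^(n−k).

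| Assumed grade 4-5 only | p under corrected rule | n = 40 | n = 54 |
|---|---|---|---|
| none (same as rule as written) | 0.019 | 0.007 | 0.019 |
| 0.5% | 0.024 | 0.015 | 0.041 |
| 1% | 0.029 | 0.028 | 0.071 |
| 2% | 0.039 | 0.070 | 0.159 |

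Under the rule as written the first line applies whatever the grade 4-5 rate. Only the direction is secure; the sizes follow from the assumed rates.

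**Step 4: cohort scope.** Four subjects are 4/40 = 10.0% of the Cohort 2 experimental arm if the count starts afresh, and 4/(54 + 40) = 4/94 = 4.3% if Cohort 1 is included. If Cohort 1 had no qualifying event, the two counts coincide.

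**The case against.** The strongest reply is that this is a slip of wording whose intent is plain and whose consequences are limited. Grade 3 or higher is very probably what was meant. A related grade 4 or 5 event would often meet the SAE definition in section 14.4.2 and so reach the medical monitor and the DSMC quickly. The committee that sees the stopping-rule count also sees the severe events. Section 14.3 allows a stop after a single event. Late deaths are covered too: "any death which occurs more than 30 days after protocol treatment has ended but which is felt to be treatment related, must be reported". The gap therefore matters only if fewer than four subjects ever have a grade 3 event, grade 4-5-only subjects would bring the total to four, and neither the DSMC nor the principal investigator acts.

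Most of this stands, and it limits the practical risk. It does not repair the rule. The section 14.3 stop is for unexpected safety issues and rests on judgement; SAE reporting sets no number; neither alters what section 9.4 counts. That the intent is plain is a reason to write it down.

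Three stronger readings are tempting, and the documents do not support them.

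- A reader might infer that severe late toxicity escapes oversight, because SAE evaluation "will continue until the first follow up visit, 28 days (+/- 14) after the completion of study treatment" and the committee's full toxicity review covers only patients on treatment or within 30 days of it. But section 9.4 is triggered by related toxicities, not by SAEs, and these are collected for 12 months. The length of the SAE window does not measure this defect and would not change with the fix.
- A reader might infer that the count naturally runs across both cohorts because the sentence contains no reset. The Cohort 1 heading over section 9 tells against that; the text leaves the matter open.
- A reader might infer that the rule misfired in Cohort 1. The documents report no event counts.

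**Conclusion.** The point holds. The only fixed toxicity threshold in the protocol omits subjects whose only related event is grade 4 or 5, so as written it can leave the trial open in a case worse than one that closes it. This is an incorrect decision threshold, not merely missing detail.

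Its practical weight is modest. The gap is confined to subjects with no related grade 3 event, discretionary oversight remains in place, and the primary quality-of-life analysis is not affected. The change in closure probability cannot be stated from the documents.

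The conclusion rests on the literal wording of section 9.4 and on the absence of any other text that makes grade 3 a floor. With Cohort 1 enrolled and analysed, the forward value of the correction depends mainly on the rule applying to the 40 experimental-arm patients planned for Cohort 2. Section 4.2 and the reference to closing the trial suggest that it does, but no section says so. The cohort question is a clarification, not a second error.

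**What to change.** In section 9.4, change *grade 3* to *grade 3 or higher*. In the same amendment, state that the rule applies to Cohort 2 and whether Cohort 1 events count towards the four. For example: *The trial closes once four different experimental-arm subjects [in Cohort 2 / in Cohorts 1 and 2 together] have had a vaginal, rectal or bladder toxicity of grade 3 or higher attributed to brachytherapy.* The choice in brackets is for the sponsor and the DSMC.

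The cost is one sentence and the IRB approval that section 14.6 requires for any amendment. Grade and relationship to treatment are already recorded for every adverse event, so no additional data collection is needed.
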